10.1.2 Disease Parameters

Measurable disease. Measurable disease is the presence of at least one (1) lesion that can be accurately measured in at least one dimension with longest diameter >20 millimeters (mm) using conventional techniques (CT, MRI, x-ray) or >10 mm with spiral CT scan. Measurable lesions must be at least 2 times the slice thickness in mm. All tumor measurements must be recorded in millimeters (or decimal fractions of centimeters).

A lesion in a previously irradiated area is not eligible for measurable disease unless there is objective evidence of progression of the lesion prior to study enrollment. Lesions in previously irradiated areas must be clearly identified as such.

Malignant lymph nodes: To be considered pathologically enlarged and measurable, a lymph node must be ≥ 15 mm in short axis when assessed by CT scan (CT scan slice thickness recommended to be no greater than 5 mm). At baseline and in follow-up, only the short axis will be measured and followed.

Non-measurable disease: All other lesions (or sites of disease), including small lesions (longest diameter <10 mm or pathological lymph nodes with ≥ 10 to < 15mm short axis, are considered non-measurable disease. Bone lesions, leptomeningeal disease, ascites, pleural/pericardial effusions, lymphangitis cutis/pulmonis, inflammatory breast disease, abdominal masses identified by

physical exam that are not measurable by reproducible imaging techniques, and cystic lesions are all considered non-measurable.

Target lesions: All measurable lesions up to a maximum of 2 lesions per organ and 5 lesions in total, representative of all involved organs, should be identified as target lesions and recorded and measured at baseline. Lesions must be accurately measured in 1 dimension with a minimum size of 10 mm by CT or MRI (slice thickness no greater than 5 mm), 20 mm by *chest* x-ray. Nodes must have a short axis ≥ 15 mm. The short axis should be included in the sum of the lesions in the calculation of response. Nodes that shrink to < 10 mm are considered normal. Target lesions should be selected on the basis of their size, be representative of all the involved organs, and should be lesions that can be followed with reproducible repeated measurements.

Lytic bone lesions or mixed lytic-blastic lesions, *with identifiable soft tissue components*, that can be evaluated by cross sectional imaging techniques such as CT or MRI can be considered target lesions if the *soft tissue component* meets the definition of measurability as defined above. Cystic lesions thought to represent cystic metastases can be considered as target lesions. However, if non-cystic lesions are present, these are preferred for selection as target lesions. Lesions in previously irradiated areas or areas subject to other loco-regional therapy are usually not considered measurable unless there has been demonstrated progression of that lesion.

Non-target lesions: All other lesions, including small lesions < 10 mm or pathological lymph nodes measuring ≥ 10 mm to < 15 mm in short axis, as well as truly non-measurable lesions, which include leptomeningeal disease, ascites, pleural or pericardial effusion, inflammatory breast disease, lymphangitic involvement of skin or lung, abdominal masses identified by physical exam that are not measurable by reproducible imaging techniques.

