3.1 Eligibility Criteria

Participants must meet the following criteria on screening examination to be eligible to participate in the study:

- 3.1.1 Participants must have histologically confirmed advanced malignancy that is metastatic and/or unresectable and/or recurrent with confirmed inactivating mutations in TSC1 or TSC2 or activating MTOR mutations, identified in any

CLIA-certified laboratory. All genetic findings must be reviewed by the study PI, [name], prior to study entry.

Biopsy of a primary or metastatic lesion must have been performed within the past two years. Sufficient pathologic material must be available to enable whole exome sequencing at the time of study entry. Patients with biopsy samples older than 2 years must undergo a fresh tumor biopsy or should receive approval for enrollment from the Principal investigator.

- 3.1.2 Participants must have measurable disease, defined as at least one lesion that can be accurately measured in at least one dimension (longest diameter to be recorded for non-nodal lesions and short axis for nodal lesions) as ≥ 20 mm with conventional techniques or as ≥ 10 mm with spiral CT scan, MRI, or calipers by clinical exam. See Section 10 for the evaluation of measurable disease.
- 3.1.3 Participants may have received any number of prior therapies, from 0 to > 10 . Prior treatment with PI3-kinase or mTOR inhibitors is not permitted, unless they were given as adjuvant therapy without undue toxicity, and without suggestion of resistance to therapy.
- 3.1.4 Age ≥ 18 years.
- 3.1.5 ECOG performance status ≤ 2 (see Appendix A).
- 3.1.6 Participants must have normal organ and marrow function as defined below:
- Leukocytes $\geq 3,000/\text{mcL}$
 - Absolute neutrophil count $\geq 1,500/\text{mcL}$
 - Platelets $\geq 100,000/\text{mcL}$
 - Hemoglobin ≥ 9.0 gr/dL
 - total bilirubin ≤ 1.5 X the institutional upper limit of normal (ULN)
 - AST (SGOT)/ALT (SGPT) ≤ 2.5 X institutional upper limit of normal.
Patients with confirmed liver metastases are permitted to have AST/ALT at levels ≤ 5 X the institutional upper limit of normal (ULN)
 - creatinine ≤ 1.5 X the institutional upper limit of normal (ULN)
 - Total cholesterol < 300 mg/dL
 - Triglycerides < 250 mg/dL

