10.1.1 Definitions

Evaluable for toxicity: All participants who receive at least one dose of study treatment will be evaluable for toxicity from the time of their first treatment.

Evaluable for objective response: Only those participants who have measurable disease present at baseline, have received at least one cycle of therapy, and have had their disease re-evaluated will be considered evaluable for response. These participants will have their response classified according to the definitions stated below. (Note: Participants who exhibit objective disease progression or die prior to the end of cycle 1 will also be considered evaluable.)

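### Measurable disease is defined differently for entry (3.1.2), target selection (10.1.2) and response evaluability (10.1.1), so an eligible patient may have no measurable disease

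*Combined protocol and SAP*

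**What the plan says.** **Entry.** Section 3.1.2 requires at least one lesion measuring "≥ 20 mm with conventional techniques or as ≥ 10 mm with spiral CT scan, MRI, or calipers by clinical exam". The measurement is the longest diameter for non-nodal lesions and the short axis for nodes, with the same limits for both. The criterion refers to Section 10 for measurability. Section 5.2 accepts contrast-enhanced CT or MRI at baseline.

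**Measurable disease.** Section 10.1.2 asks for "longest diameter >20 millimeters (mm) using conventional techniques (CT, MRI, x-ray) or >10 mm with spiral CT scan", so MRI falls under the 20 mm limit. Nodes need a short axis of at least 15 mm on CT, and nodes of 10 to under 15 mm are listed as non-measurable. The same list ends "and cystic lesions are all considered non-measurable".

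**Target lesions.** Still in 10.1.2, targets are drawn from "All measurable lesions up to a maximum of 2 lesions per organ and 5 lesions in total", but the size minimum is now 10 mm by CT or MRI (slices no thicker than 5 mm), 20 mm by chest x-ray and 15 mm short axis for nodes. The section goes on: "Cystic lesions thought to represent cystic metastases can be considered as target lesions". It adds: "However, if non-cystic lesions are present, these are preferred for selection as target lesions".

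**Evaluability and decision.** Section 10.1.1 opens its response-evaluable definition with "Only those participants who have measurable disease present at baseline". Section 14.1 stops the TSC1/TSC2 cohort at 3 or fewer responses in 21 patients and declares success at 8 or more responses among the 50 registered.

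**The concern.** Objective response is the primary endpoint, and partial response is a 30% fall in the sum of target diameters. Measurability therefore decides who enters, which lesions make up the baseline sum, and who is evaluable. One definition should serve all three purposes. Here the entry criterion points to a definition stricter than itself for MRI and for nodes, and that definition differs from the target-lesion rule in its own section. Two sites could treat the same kind of patient differently, each citing the protocol.

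**Working it through.** **1. The rules side by side**

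| Lesion | 3.1.2 (entry) | 10.1.2, measurable / non-measurable | 10.1.2, target lesions |
|---|---|---|---|
| Non-nodal, MRI | ≥ 10 mm | > 20 mm | 10 mm minimum |
| Non-nodal, spiral CT | ≥ 10 mm | > 10 mm | 10 mm minimum by CT |
| Superficial, calipers | ≥ 10 mm | no limit given | no limit given |
| Node, short axis | ≥ 10 mm (spiral CT or MRI) | ≥ 15 mm | ≥ 15 mm |
| Suspected cystic metastasis | not mentioned | non-measurable | allowed; non-cystic preferred |

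**2. What follows for a patient** (lesion sizes are assumptions for illustration)

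- Only lesion 18 mm on MRI, non-nodal. Since 18 ≥ 10, the patient is eligible. Since 18 is not above 20, there is no measurable disease by the definition, and the patient is not evaluable under 10.1.1. The lesion nevertheless meets the target-lesion minimum. If it shrank to 12 mm, the change would be (12 − 18)/18 = −33.3%, a partial response once confirmed.
- Only lesion a node of 12 mm short axis on spiral CT. Since 12 ≥ 10, the patient is eligible. Since 12 < 15, the node is non-measurable. Here 10.1.2 agrees with itself, and the conflict is with 3.1.2.
- Only cystic metastases above the size limit. Measurable disease is absent under the non-measurable list, while the later sentence permits these lesions as targets.

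**3. The design figures in 14.1**

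With X1 the responses in the first 21 patients and X2 those in the next 29:

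- P(early stop) = P(X1 ≤ 3), at a 10% rate = 0.848 (stated 85%).
- P(success) = Σ over x ≥ 4 of P(X1 = x) × P(X2 ≥ 8 − x) = 0.912 at 30% (stated 91%) and 0.066 at 10% (stated 0.07).

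All three reproduce, so the fault lies in the endpoint definition and not in these figures.

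**4. Sensitivity**

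The documents do not give the share m of patients whose only lesions are disputed. Assume that these patients would respond at the same rate as others, but all count as non-responders among those registered. The effective target rate is 0.30 × (1 − m).

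| m (assumed) | Effective rate | Power |
|---|---|---|
| 0% | 0.300 | 91.2% |
| 5% | 0.285 | 88.6% |
| 10% | 0.270 | 85.3% |
| 15% | 0.255 | 81.2% |
| 20% | 0.240 | 76.4% |

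**5. How often one patient could matter at stage 1**

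One reclassified patient can change the stage 1 decision when the count is 3 or 4. P(X1 = 3) + P(X1 = 4) is about 30% at a true rate of 10%, 41% at 20% and 17% at 30%. This is the chance of being at the boundary, not the chance that a disputed patient is present.

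**The case against.** **The MRI conflict is one outlying sentence.** The 10 mm limit appears in 3.1.2 and in the paragraph that builds the baseline sum, and the small-lesion cut-off in the non-measurable list is also below 10 mm. This shows what was probably intended. It does not remove the conflict, because the outlier is the definition of measurable disease, and 10.1.1 turns on that term.

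**The cystic sentence can be read as an exception.** Bone lesions are likewise listed as non-measurable, and lytic lesions with a soft-tissue component are then admitted as targets. The later list of truly non-measurable lesions omits both bone and cystic lesions. This reading is plausible and makes the cystic part the weakest of the three. However, the bone exception states that the soft-tissue component must meet the measurability definition, and the cystic sentence carries no such condition.

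**A reader might infer that one patient can be a responder or stable depending on whether a cyst is a target.** Take a solid lesion going from 30 to 18 mm and a cystic metastasis from 40 to 38 mm. With both as targets, the sum falls from 70 to 56 mm: (56 − 70)/70 = −20%, stable disease. With the solid lesion alone, (18 − 30)/30 = −40%, partial response. The stated preference for non-cystic targets largely settles this in favour of the solid lesion. A preference leaves some discretion, but the example is not good evidence of a contradiction.

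**A threshold rule is always sensitive to one patient.** That is true, so step 5 shows only why the definition deserves care and does not measure the harm.

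**Conclusion.** The inconsistency is real, bears on the primary endpoint and should be corrected. The firm parts are the MRI limit (10 to 20 mm: eligible, yet without measurable disease) and the nodal limit (10 to under 15 mm short axis: the same result). The cystic conflict is genuine on the face of the text but may be an unmarked exception.

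The size is unknown, because the documents do not say how many patients have only such lesions. The fall in power from 91% to 85% or 76% rests on assumed shares of 10% and 20%, with every such patient counted as a non-responder.

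A reader might also infer that the same patient can generally be a responder, a non-responder or not evaluable. The documents do not support that as a general statement. All three outcomes need a patient with assumed sizes and both kinds of disputed lesion at once. For the final rule, moreover, a non-evaluable patient is still among the 50 registered and simply adds no response.

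**What to change.** Use a single definition of measurable disease in 10.1.2, in place of the present measurable-disease sentence, and make 3.1.2 and 10.1.1 refer to it. Its limits are already in the protocol:

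- at least 10 mm by CT or MRI with slices of 5 mm or less, otherwise at least twice the slice thickness;
- at least 20 mm by chest x-ray;
- at least 15 mm short axis for nodes;
- at least 10 mm by calipers for superficial lesions, carried over from 3.1.2.

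In the non-measurable list, except suspected cystic metastases that meet the size limit. Keep the present preference for non-cystic targets as a preference. An outright ban could conflict with the requirement that targets represent all involved organs, where an organ has only cystic metastases.

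State that benign simple cysts are not disease, so they are neither target nor non-target lesions. Listing them as non-measurable disease would make them non-target lesions, and their persistence could then block a complete response.

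The cost is an amendment to wording, with no extra scans, readers or patients.

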10.1.3 Methods for Evaluation of Measurable Disease

All measurements should be taken and recorded in metric notation, using a ruler, calipers, or digital measurement tool. All baseline evaluations should be performed as closely as possible to the beginning of treatment and never more than 4 weeks before the beginning of the treatment.

The same method of assessment and the same technique should be used to characterize each identified and reported lesion at baseline and during follow-up. Imaging-based evaluation is preferred to evaluation by clinical examination when both methods have been used to assess the anti-tumor effect of a treatment.

Clinical lesions. Clinical lesions will only be considered measurable when they are superficial (e.g., skin nodules and palpable lymph nodes). For the case of skin lesions, documentation by color photography, including a ruler to estimate the size of the lesion, is recommended.

Chest x-ray. Lesions on chest x-ray are acceptable as measurable lesions when they are clearly defined and surrounded by aerated lung; however, CT is preferable.

Conventional CT and MRI: This guideline has defined measurability of lesions on CT scan based on the assumption that CT thickness is 5mm or less. If CT scans have slice thickness greater than 5 mm, the minimum size of a measurable lesion should be twice the slice thickness. MRI is also acceptable in certain situations (e.g. for body scans).

Use of MRI remains a complex issue. MRI has excellent contrast, spatial, and temporal resolution; however, there are many image acquisition variables involved in MRI, which greatly impact image quality, lesion conspicuity, and measurement. Furthermore, the availability of MRI is variable globally. As with CT, if an MRI is performed, the technical specifications of the scanning sequences used should be optimized for the evaluation of the type and site of disease. Furthermore, as with CT, the modality used at follow-up should be the same as was used at baseline and the lesions should be measured/assessed on the same pulse sequence. It is beyond the scope of the RECIST guidelines to prescribe specific MRI pulse sequence parameters for all scanners, body parts, and diseases. Ideally, the same type of scanner should be used and the image acquisition protocol should be followed as closely as possible to prior scans. Body scans should be performed with breath-hold scanning techniques, if possible.

Ultrasound (US): When the primary endpoint of the study is objective response evaluation, US should not be used to measure tumor lesions. It is, however, a possible alternative to clinical measurements of superficial palpable lymph nodes, subcutaneous lesions, and thyroid nodules. US might also be useful to confirm the complete disappearance of superficial lesions usually assessed by clinical examination.

FDG PET and PET/CT. The acquisition of FDG PET and FDG PET/CT scans should follow the NCI Guidelines for using FDG PET as an indicator of therapeutic response (L.K. Shankar, J.M. Hoffman, S. Bacharach, M.M. Graham, J. Karp, A.A. Lammertsma, S. Larson, D.A. Mankoff, B.A. Siegel, A. Van den Abbeele, J. Yap, D. Sullivan. Consensus recommendations for the use of 18F-FDG PET as an indicator of therapeutic response in patients in National Cancer Institute Trials. J Nucl Med, 47(6):901-903, 2006). Patients should avoid strenuous exercise and be on a low carbohydrate diet for 24 hours prior to the

scan. Patients should fast for 4 hours or longer prior to the FDG injection and should have serum glucose of less than 200 mg/dL at the time of FDG injection. A 10-20 mCi dose of FDG should be injected for typical adult patients. For longitudinal studies with multiple scans, particular attention should be paid to ensure consistent patient preparation and acquisition parameters between the follow-up scan and the baseline scan. When designing a study where PET scans are going to be utilized as one of the modalities to evaluate efficacy, it is important to consult with physicians in nuclear medicine in designing the appropriate criteria to be utilized.

Endoscopy, Laparoscopy: The utilization of these techniques for objective tumor evaluation has not yet been fully and widely validated. Their uses in this specific context require sophisticated equipment and a high level of expertise that may only be available in some centers. Therefore, the utilization of such techniques for objective tumor response should be restricted to validation purposes in reference centers. However, such techniques may be useful to confirm complete pathological response when biopsies are obtained.

Tumor markers. Tumor markers alone cannot be used to assess response. If markers are initially above the upper normal limit, they must normalize for a subject to be considered in complete clinical response. Specific additional criteria for standardized usage of prostate-specific antigen (PSA) and CA-125 response in support of clinical trials are being developed.

Cytology, Histology: These techniques can be used to differentiate between partial responses (PR) and complete responses (CR) in rare cases (e.g., residual lesions in tumor types, such as germ cell tumors, where known residual benign tumors can remain).

The cytological confirmation of the neoplastic origin of any effusion that appears or worsens during treatment when the measurable tumor has met criteria for response or stable disease is mandatory to differentiate between response or stable disease (an effusion may be a side effect of the treatment) and progressive disease.

10.1.4 Response Criteria

10.1.4.1 Evaluation of Target Lesions

Complete Response (CR):

Disappearance of all target lesions: Any pathological lymph node must have reduction in short axis to < 10 mm.

Partial Response (PR):

At least a 30% decrease in the sum of the diameters of target lesions, taking as reference the baseline sum diameters.

Progressive Disease (PD):

At least a 20% increase in the sum of the diameters of target lesions, taking as reference the smallest sum with at least 5mm absolute increase in the sum of all lesions. The appearance of one or more new lesions* denotes disease progression.

Stable Disease (SD):

Neither sufficient shrinkage to qualify for PR nor sufficient increase to qualify for PD, taking as reference the smallest sum diameters while on study.

Unknown (UN): Assessment of target lesions cannot be made due to insufficient or unevaluable data. In this case, a concise explanation must be given.

Note: If tumor response data is missing for target lesions, the overall assessment must be UN unless there is new disease that would result in an overall assessment of PD. However, if there is missing or unevaluable data for non-target lesions, but data is available for all target lesions, the overall response for that time point will be assigned based on the sum LD of all target lesions. Additionally, the assessment of CR cannot be made if there is missing or unevaluable data for non-target lesions. In this case, the overall assessment would be PR.

***Definition of New Lesion:** The finding of a new lesion should be unequivocal (i.e. not due to difference in scanning technique, imaging modality, or findings thought to represent something other than tumor (ex: new bone lesions may be healing or flare of pre-existing lesions). However, a lesion identified on a follow-up scan in an anatomical location that was not scanned at baseline is considered new and will indicate PD. If a new lesion is equivocal (because of small size, etc.), follow-up evaluation will clarify if it truly represents new disease and if PD is confirmed, progression should be declared using the date of the initial scan on which the lesion was discovered.

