10.1.4.2 Evaluation of Non-Target Lesions

Complete Response (CR): Disappearance of all non-target lesions and

normalization of tumor marker level. All lymph nodes must be non-pathological in size (< 10 mm short axis).

Note: If tumor markers are initially above the upper normal limit, they must normalize for a subject to be considered in complete clinical response.

Incomplete Response/Stable Disease (SD): Persistence of one or more non-target lesions and/or maintenance of tumor marker level above the normal limits.

Progressive Disease (PD): Appearance of one or more new lesions* (new lesions must be > slice thickness) and/or unequivocal progression of existing non-target lesions. Overall level of substantial worsening that merits discontinuation of therapy. A useful test that can be applied when assessing non-targets for unequivocal progression is to consider if the increase in overall disease burden based on the change in non-measurable disease is comparable in magnitude to the increase that would be required to declare PD for measurable disease.

Unknown (UN): Assessment of non-target lesions cannot be made due to insufficient or unevaluable data. In this case, a concise explanation must be given.

***Definition of New Lesion:** The finding of a new lesion should be unequivocal (i.e. not due to difference in scanning technique, imaging modality, or findings thought to represent something other than tumor (ex: new bone lesions may be healing or flare of pre-existing lesions). However, a lesion identified on a follow-up scan in an anatomical location that was not scanned at baseline is considered new and will indicate PD. If a new lesion is equivocal (because of small size, etc.), follow-up evaluation will clarify if it truly represents new disease and if PD is confirmed, progression should be declared using the date of the initial scan on which the lesion was discovered.

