10.1.6 Progression-Free Survival

Progression-Free Survival (PFS) is defined as the duration of time from study registration to the date of documented disease progression or death, whichever occurs first. Patients not experiencing an event will be censored at the date of the last disease assessment.

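### The missing-data note in Section 10.1.4.1 scores some progressing scans as Unknown, against Section 10.1.4.2 and the response table, and so misdates progression

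*Combined protocol and SAP*

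**What the plan says.** Section 10.1.4.1 defines target-lesion PD as growth of at least 20%, and at least 5 mm, over the smallest sum. It reserves UN for the case "Assessment of target lesions cannot be made due to insufficient or unevaluable data". A note then sets the overall assessment: "If tumor response data is missing for target lesions, the overall assessment must be UN unless there is new disease" that would itself lead to PD. In that section new disease means a new lesion; of an equivocal one it says that "follow-up evaluation will clarify if it truly represents new disease". The note's next sentence covers the reverse case, missing non-target data: "but data is available for all target lesions, the overall response for that time point will be assigned" from the target-lesion sum.

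Section 10.1.4.2 lists two routes to non-target PD: new lesions and/or "unequivocal progression of existing non-target lesions". Neither depends on target data.

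The table for measurable disease in 10.1.4.3 gives overall PD when non-target status is PD, for any target status and whether or not there are new lesions. It also gives overall PD when target status is PD, whatever the other columns show. A footnote to the non-target row says that such progression may be accepted exceptionally. The companion table for non-measurable disease gives PD for unequivocal non-target progression, with no such footnote.

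Sections 10.1.6 and 14.1 end PFS at documented progression or death. Otherwise, "Patients not experiencing an event will be censored at the date of the last disease assessment". Sections 10.1.5 and 14.1 end duration of response at documented progression.

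**The concern.** The same scan can receive two different overall assessments, depending on which part of Section 10 the assessor follows, and no text ranks one part above another. Two sites could therefore date progression differently from identical findings.

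The error runs in one direction. The note can turn a PD into a UN but never the reverse. A UN is not a progression event, so PFS and duration of response can only lengthen. With no control arm, nothing offsets this.

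**Working it through.** The plan states no figure on this point, so there is none to reproduce. The check sets the note against 10.1.4.2 and the 10.1.4.3 table for each combination of findings when target data are incomplete.

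| Target data | Non-target | New lesion | Note in 10.1.4.1 | 10.1.4.2 and table |
|---|---|---|---|---|
| Wholly missing | PD | No | UN | PD (footnote: exceptional) |
| Wholly missing | PD | Yes | PD | PD |
| Wholly missing | Not PD | No | UN | No PD row applies |
| Wholly missing | Not PD | Yes | PD | PD |
| Partly missing, measured lesions already meet PD | PD | No | UN | PD |
| Same | PD | Yes | PD | PD |
| Same | Not PD | No | UN | PD |
| Same | Not PD | Yes | PD | PD |

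Three of the eight rows conflict: the first, fifth and seventh. The first follows from the wording directly. The other two require that missing includes partly missing.

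**Why partly missing data can still prove PD.** A diameter cannot be negative, so the full sum is at least the sum of the measured lesions. Illustration with assumed diameters:

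- Five target lesions with a smallest sum of 5 × 20 = 100 mm.
- At the next scan one lesion is not imaged and the other four measure 32 + 30 + 30 + 30 = 122 mm.
- Full sum ≥ 122 mm; increase ≥ 122 − 100 = 22 mm, which exceeds 5 mm.
- Relative increase ≥ 22/100 = 22%, which exceeds 20%.

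The PD definition in 10.1.4.1 is met whatever the missing diameter. The section's own UN definition is not met, because the assessment can be made. The note would still require UN.

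**Effect on dates.** Section 10 schedules response scans every 8 weeks. A PD scored UN produces no PFS event at that scan. The event is then recorded at a later scan or at death, or the patient is censored. Duration of response, defined to end at documented progression, also runs on. PD recorded at an earlier scan is not undone.

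**Effect on response.** UN and PD are both non-responses at that visit. An indirect route exists: 10.1.4.3 counts best response until progression, so a response seen after an unrecorded PD could be credited.

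**The case against.** **The footnote.** The table itself treats progression in non-target lesions alone as exceptional and permissive, so the conflict concerns part of an already uncommon category. This stands as a limit on how often the problem arises. It does not remove the conflict, because the note accepts such progression in no circumstances, and 10.1.4.2 carries no such restriction.

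**Whether the table covers missing target data.** It has no UN row for target lesions, so one could argue that its entry for any target status was never meant to include missing. But the row giving PD for a new lesion uses the same entry, and the note agrees with that row when target data are missing. Nor does 10.1.4.2 make non-target PD depend on target data.

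**Partly missing data.** It can be said that UN applies only when no assessment is possible, so a proven target PD is simply PD. That is the sensible reading of the definition, but the note's contrast with data on all target lesions points the other way. This limb remains conditional. It conflicts with 10.1.4.1's own definitions and the table's target-PD row, not with 10.1.4.2, which covers non-target lesions only.

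**Stronger readings that the documents do not support.** A reader might infer that progressing patients leave the response denominator, so that 15/50 = 30% becomes, say, 15/46 = 32.6%. Section 14.1 counts at least 8 responses among 50 registered patients, so a UN patient stays in as a non-responder. Section 10.1.1 does not say that UN makes a patient non-evaluable, and it adds that "Participants who exhibit objective disease progression or die prior to the end of cycle 1 will also be considered evaluable".

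A reader might also infer that losing a share q of progressions inflates the PFS median by 1/(1 − q), for example 1/0.9 = 1.11 at q = 0.10. That treats the events as lost altogether. Section 5.7 follows patients to death and death is a PFS event, so many would be delayed instead, and the documents give no basis for any q.

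A false later response is possible but needs an unlikely sequence: target lesions at least 30% below baseline, no non-target PD at that later scan, and the confirmatory scan expected at least 4 weeks afterwards.

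**Conclusion.** The contradiction is real. With target data missing, unequivocal non-target progression and no new lesion, the note requires UN while 10.1.4.2 and the table give PD. If missing includes partly missing, which the wording suggests but does not state, the note also overrides target progression that is already certain.

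The consequence is a misdated progression at that time point for PFS and duration of response, both secondary endpoints, in the direction that favours the drug. No direct effect on the primary response rate is shown, and the success rule is not changed through its denominator. The number of affected scans is unknown, so no size can be given. The point deserves correction because the rule is wrong as written and the remedy uses PD criteria already in the protocol.

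**What to change.** Replace the first sentence of the note in 10.1.4.1 with:

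> If target-lesion data are missing, the overall assessment is UN unless there is a new lesion, unequivocal progression of non-target lesions as defined in 10.1.4.2, or the measured target lesions alone already meet the PD criteria against the smallest sum; in these cases the overall assessment is PD on that date.

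Reconcile the footnote to the 10.1.4.3 table with 10.1.4.2 as well, so that 10.1.4.1, 10.1.4.2 and the table give the same result for the same scan. Changing the note alone would leave the footnote treating as exceptional what 10.1.4.2 states without restriction.

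The cost is one replaced sentence and a footnote edit, with no added scans, staff or patients. Reported PFS and duration of response may become slightly less favourable.
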